9.6.2 Laboratory Test Results

Laboratory results will be summarized for each cohort with descriptive statistics at baseline and selected time points for selected laboratory parameters. Shifts in grades of selected safety laboratory values between the baseline and the worst on-study value will be tabulated by cohort.

The number and proportion of subjects in each cohort with positive qPCR for talimogene laherparepvec DNA detection in any swab of a lesion suspected to be herpetic in origin will be calculated based on the qPCR Suspicious Lesion Swab Analysis Set.

Individual subjects having a positive qPCR results for talimogene laherparepvec DNA detection will be reviewed.

A listing will be provided for subjects by assessed time point of qPCR analysis results (positive, and numeric value if quantifiable) for talimogene laherparepvec DNA in swab samples taken from cold sore, vesicles, and other lesions suspected to be herpetic in origin.

9.6.3 Vital Signs

Descriptive statistics will be presented for systolic/diastolic blood pressure, heart rate, respiratory rate, and temperature for baseline, each post-baseline visit, change from baseline, and percent change from baseline for each cohort.

9.6.4 Physical Measurements

Physical measurements will not be analyzed.

9.6.5 Electrocardiogram

The electrocardiogram (ECG) measurements from this clinical study were performed as per standard of care for routine safety monitoring, rather than for purposes of assessment of potential QT interval corrected (QTc) effect. Because these evaluations may not necessarily be performed under the rigorous conditions expected to lead to meaningful evaluation of QTc data; neither summaries nor statistical analyses will be provided, and these data would not be expected to be useful for meta-analysis with data from other trials.

9.6.6 Antibody Formation

Baseline HSV-1 serostatus will be summarized. The incidence of HSV-1 seroconversion will be summarized for subjects that are baseline seronegative.

9.6.7 Exposure to Investigational Product

Summary statistics for exposure to talimogene laherparepvec, including total doses administered, total volume administered, duration from the first to the last administration of talimogene laherparepvec, and the average volume received by subject per visit will be provided and will be separated by the first (concentration of 10^6 PFU/ml) and subsequent doses (concentration of 10^8 PFU/ml). Subject incidence rate and reasons for IP delay and dose change/withheld will be tabulated.

Exposure to pembrolizumab including total doses (in mg) administered, relative dose intensity, duration from the first to the last administration, and the average dose received by subject per visit will be provided. Subject incidence rate and reasons for IP delay, IP interruption and dose change/withheld will be examined.

9.6.8 Exposure to Concomitant Medication

The number and proportion of subjects receiving therapies of interest will be summarized by preferred term or category for each cohort as coded by the World Health Organization Drug (WHO DRUG) dictionary.

The number and proportion of subjects receiving subsequent anti-cancer therapies will be summarized by preferred term or category for each cohort as coded by the World Health Organization Drug (WHO DRUG) dictionary.

9.7 Other Analyses

ECOG performance status scores will be summarized at each time point. Changes in scores for ECOG performance status scores from baseline will also be tabulated.

Spider plots for subject-level percent change from baseline in tumor burden by BOR per modified RECIST 1.1 and iBOR per modified irRC-RECIST and disease stage at baseline will be provided. Waterfall plots for subject-level maximum overall tumor burden reduction by BOR per modified RECIST 1.1 and iBOR per modified irRC-RECIST will also be summarized. Tumor assessments occurring after the start of the first subsequent anti-cancer therapy will be excluded from the analysis of tumor burden. With the exception of tumor assessments with an increase of tumor burden $\geq 20\%$ and also demonstrate ≥ 5 mm increase from nadir, tumor assessments occurring on or after the complete or partial removal/reduction of any target lesion with melanoma on pathology evaluation or unknown pathology results will also be excluded from the analysis of tumor burden.

10. Changes From Protocol-specified Analyses

Not applicable.

11. Literature Citations / References

Brookmeyer R and Crowley J. A confidence interval for the median survival time. *Biometrics*. 1982;38:29-41.

Clopper, C. and Pearson, E. (1934) "The Use of Confidence or Fiducial Limits Illustrated in the Case of the Binomial," *Biometrika*, 26, 404–413

Eisenhauer, A., et al (2009) "New Response Evaluation in Solid Tumors: Revised RECIST Guideline (version 1.1)", *EJC*, 45, 228-247.

[figure not shown]
Lin, Guixian, Ying So, and Gordon Johnston. "Analyzing survival data with competing risks using SAS software." *SAS Global Forum*. Vol. 2102. 2012.

[figure not shown]
Pintilie, M. (2006) *Competing Risks: A Practical Perspective*. Wiley.

<http://dx.doi.org/10.1002/9780470870709>

12. Appendices

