7.1.5 Other Treatment Procedures

Investigators may choose to resect lesions which become suitable for resection to render the subject free of macroscopic disease. Additionally, biopsies may be taken of cutaneous or subcutaneous lesions for tumor analysis during the study. However, resection of lesions may occur only following tumor assessment. If a subject undergoes resection of the lesion, the investigator or designee should notify the sponsor medical monitor as soon as possible. [REDACTED]

[REDACTED]

Local radiation treatment to the site of bone and other metastasis will be permitted for palliative pain management at any time during the study. If a subject undergoes local radiation, the investigator or designee should notify the sponsor's medical monitor as soon as possible.

If a subject demonstrates evidence of new or worsening central nervous system (CNS) metastases, all study treatments should be withheld and the investigator or designee should notify the sponsor's medical monitor as soon as possible. Subjects may be allowed to remain on study after discussion between the sponsor's medical monitor and the investigator to determine the appropriateness of treatment resumption provided CNS lesions can be treated with stereotactic radiotherapy, Gamma Knife, or craniotomy. After approval is obtained from the sponsor's medical monitor, subjects may be allowed to reinitiate talimogene laherparepvec and/or pembrolizumab treatment per Section 7.4.1, following stereotactic radiotherapy only when dosing of corticosteroid is below 1.5 mg dexamethasone, 10 mg prednisone or equivalent. If higher doses of corticosteroid are used, talimogene laherparepvec and/or pembrolizumab must be held until that dose level is reached during the period of steroid tapering.

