Merging lesions (for the current and all future assessments)	
For 2 or more target/new measurable lesions: smaller lesion = 0 mm; larger lesion, longest diameter of the merged lesion.
 
For 2 or more non-target/new non-measurable lesions: smaller lesion = absent; larger lesion = present.
 
For target/new measurable lesion and a non-target/new non-measurable lesion: non-target/new non-measurable lesion = absent; target lesion/new measurable lesion, include both merged lesions.
 
Any lesion with measurement 0 mm that resulted from merging with another lesion(s) should be documented as lesions that were combined with and not truly disappearing lesions.
	
Separating lesion (for the current and all future assessments)	
The largest measurable part of the split lesion should be considered to be the previously recorded target/new measurable lesion. The dimensions of the split parts would still be target/new measurable lesions. When a nontarget/new non-measurable lesion splits into 2 or more lesions, the split parts remain nontarget lesions. Any new lesions that result from separating should be documented as lesions that were generated by separating and not truly new lesions.
	

Page 2 of 2

* If the resected lesion contained no melanoma under pathology evaluation, subsequent tumor assessments post-procedure may be used for tumor burden calculations and/or determination of response. If the resected lesion contained melanoma or pathology results were unknown, the recorded tumor assessments post-procedure may be used for tumor burden calculations, but determination of response will be considered unable to evaluate (UE) for both modified versions of RECIST 1.1 and irRC-RECIST, except in the case of PD. If the new tumor burden post-procedure is lower than the nadir before the procedure, the new nadir will be set to the post-procedure tumor burden. Otherwise, the previous pre-procedure nadir will be retained as the nadir and subsequent assessments for PD will be determined from the nadir.

Modified RECIST v1.1

RECIST v1.1 will be used with the following modifications to the guidelines as defined by Eisenhauer et al, 2009:

- Increased total target lesions to a maximum of 10 (up to a maximum of 5 per organ).
- Target lesions must be measurable by CT or MRI only; lesions not measurable by CT or MRI (ie, assessed via other imaging modalities or clinical measurements) are considered as non-target.

Table 12-4. Evaluation of Target Lesions

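### The tumour-burden plots in SAP 9.7 can show surgical removal of a lesion as the subject's best shrinkage, because progression scans kept after resection are judged against a nadir that the surgery lowered

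*SAP*

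**What the plan says.** SAP 9.7 plans two subject-level displays. One is "Spider plots for subject-level percent change from baseline in tumor burden", so its reference is baseline. The other is described as follows: "Waterfall plots for subject-level maximum overall tumor burden reduction by BOR per modified RECIST 1.1 and iBOR per modified irRC-RECIST will also be summarized".

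The section then excludes "tumor assessments occurring on or after the complete or partial removal/reduction of any target lesion with melanoma on pathology evaluation or unknown pathology results". The sentence containing that exclusion opens with an exception, "With the exception of tumor assessments with an increase of tumor burden", set at 20% or more together with a rise of at least 5 mm from nadir. The SAP does not define nadir.

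Protocol Appendix 10 (Section 12.10) supplies what is missing. Table 12-3 gives a completely resected target lesion a diameter of 0 mm. The table's footnote allows post-procedure measurements to enter the burden calculation and adds: "If the new tumor burden post-procedure is lower than the nadir before the procedure, the new nadir will be set to the post-procedure tumor burden". If the post-procedure burden is not lower, the earlier nadir stands. Table 12-7 likewise treats nadir as the lowest burden recorded.

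Resection on study is permitted by Protocol 7.1.5: "Investigators may choose to resect lesions which become suitable for resection to render the subject free of macroscopic disease".

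**The concern.** The exclusion in SAP 9.7 appears intended to stop surgery from being drawn as drug-induced shrinkage. The exception partly undoes it, because it tests one quantity and plots another. A scan is kept because it has risen from a nadir that the operation may have lowered. It is then plotted as change from baseline, with the resected lesion counted as zero.

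SAP Section 5 uses a similar exception when deriving BOR and iBOR, and there it does no harm: only the category of progression enters, and progression cannot improve a best response. In SAP 9.7 the millimetre value enters a maximum-reduction statistic, where it can.

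At stake is the apparent depth of response. For a subject with a pre-operative reduction on record, the waterfall error can only deepen the bar. With cohorts of 15 to 27 subjects, a single misleading bar is easy to see and easy to over-read.

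**Working it through.** There is no planned figure to reproduce, since this is a data-handling rule. All millimetre values below are assumed for illustration; the documents give no subject data.

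**Notation.** B is baseline burden. N is the lowest burden recorded before the operation, baseline included. P is the post-operative burden and S is a later scan.

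**Rules applied**
- Nadir after surgery = P if P < N, otherwise N (Table 12-3 footnote).
- S is kept if S ≥ 1.2 × nadir and S − nadir ≥ 5 mm (SAP 9.7).
- Plotted value = 100 × (S − B)/B (SAP 9.7).

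**When the bar is distorted.** With the reset, the smallest scan that can be kept is max(1.2P, P + 5). It lies below every pre-operative value when max(1.2P, P + 5) < N. That means P is more than 16.7% below N (1 − 1/1.2 = 0.167) and also more than 5 mm below it. The 5 mm condition governs once P is under 25 mm, because 1.2 × 25 = 25 + 5 = 30.

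Without the reset, a kept scan must be at least 1.2N. It can then neither create nor deepen a reduction.

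**Worked cases (mm, B = 100)**

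| Pre-op scans | Removed | P | S | Rise from reset nadir | Plotted | Best pre-op |
|---|---|---|---|---|---|---|
| 98 | 58 | 40 | 50 | +25%, +10 mm | -50% | -2% |
| 95, 90 | 65 | 25 | 31 | +24%, +6 mm | -69% | -10% |
| 60, 70 | 50 | 20 | 25 | +25%, +5 mm | -75% | -40% |

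In the first row, max(48, 45) = 48, which is below 98, so the condition is met. Against the unreset nadir of 98 the same scan is 50/98 − 1 = -49%, so it would not be kept. None of the three scans is kept without the reset.

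**Dependence on the amount removed** (B = N = 100, smallest scan that is kept)
- 10% removed: P = 90, S = 108, plotted +8%. No distortion.
- 25% removed: P = 75, S = 90, plotted -10%.
- 50% removed: P = 50, S = 60, plotted -40%.
- 75% removed: P = 25, S = 30, plotted -70%.

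**Case without a reset.** Pre-operative scans 60 then 100, 30 removed, P = 70. The nadir stays at 60. A scan of 75 is +25% and +15 mm, so it is kept and plots at -25%. It does not displace the earlier -40% in the waterfall. The spider line, however, still falls from 0% to -25% because of the operation.

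**The case against.** The best counter-argument is that SAP 9.7 does not mention a reset. Post-resection scans are excluded from the burden analysis, so the nadir inside that analysis could be the pre-resection one. The waterfall problem would then disappear. It is true that the SAP is silent. But the pre-resection reading is written nowhere, and the only nadir rule in the documents points the other way. The footnote's reset was written for calling progression, which is exactly the test that the exception applies.

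Second, Protocol 7.1.5 speaks of surgery that clears all macroscopic disease, and Protocol 7.1.7 otherwise bars melanoma surgery. The worked cases leave residual disease. That limits how often they are likely to arise. Even so, Table 12-3 and SAP 9.7 both provide for partial removal, and SAP 9.7 applies as soon as any one target lesion is removed.

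Third, the plots are descriptive and are displayed by BOR or iBOR, so a deep bar labelled stable disease would look discordant. This stands, and it limits the importance of the point. Nothing planned would tell the reader that surgery is the reason.

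A reader might also infer that complete clearance gives the deepest false bars of all. The documents do not establish this. The nadir would be 0 mm and a percentage rise from it is undefined. Under modified RECIST 1.1 a new lesion does not enter the target sum, so the sum would not rise. New measurable lesions count towards burden only under modified irRC-RECIST.

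**Conclusion.** The point holds for the two tumour-burden plots. Read with the protocol's nadir rule, SAP 9.7 lets a progression scan after resection supply the waterfall's maximum reduction, and it draws a surgical drop in the spider plot. In the illustrations the bar moves from -2% to -50%, from -10% to -69% and from -40% to -75%. Removing about 10% of the burden causes no waterfall distortion.

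This rests on the plots using the protocol's nadir, on resected lesions being scored 0 mm, and on a resection that takes P far enough below N. The documents do not say how many subjects were resected, so the number affected is unknown and may be zero.

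Two wider conclusions are not supported. One is that response rates are inflated: after such a resection SAP Section 5 admits only progression into BOR and iBOR, so ORR and BOR are untouched, as are the time-to-event endpoints. The other is that each affected subject raises the share with at least a 30% reduction. No such share is planned, a 25% removal can plot at only -10%, and a subject already beyond -30% would add nothing.

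**What to change.** In SAP 9.7:
- Take the waterfall's maximum reduction only from assessments before resection of a target lesion that held melanoma or had unknown pathology, with no exception for progression.
- In the spider plot, end the line at the last assessment before that resection and mark later progression with a symbol.

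For the waterfall alone, an equivalent wording is that the exception is judged against the pre-resection nadir. That wording would not by itself take the surgical step out of the spider line, as the case without a reset shows.

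Leave the progression exception in the BOR and iBOR rules as it is. Do not carry resected lesions forward at their pre-resection diameter: that would contradict the 0 mm rule in Table 12-3 and create a second definition of burden.

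The cost is a short rewording of SAP 9.7 and a small programming change. Resected subjects get somewhat shorter spider lines. The symbol still shows that progression occurred, although the burden measured at that visit is no longer drawn.

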Appendix A. Reference Values/Toxicity Grades

Appendix B. Technical Detail and Supplemental Information Regarding Statistical Procedures and Programs

B.1 Clopper-Pearson Exact Confidence Interval

```
proc freq data=data1;  
tables var1/ binomial(exact);  
run;
```

B.2 Non-parametric cumulative incidence function (CIF)

```
proc lifetest data=event_data outcif=cif plots=cif(test);  
time timevar*cnsr(1)/eventcode=0;  
ods output;  
run;
```

Variable cnsr:

Value 0 = █████ progression event
1 = censored
2 = competing risk event
